3.3 Estimate sample size

This study is a non-inferiority study, with postoperative complications as primary outcome. According to the relevant studies, the postoperative complication rate of laparoscopic total gastric surgery is about 15%. In this study, it was assumed that the

postoperative complication rate of the study group was similar to the control group, with $\alpha=0.05$, $\beta=0.2$, and the non-inferiority threshold value set as 15%. PASS 11 was used for calculation, and the sample size of each group was 68 cases. Considering that the maximum detachment rate of this clinical study was 10%, the final sample size was 75 cases in each group.

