9.4 Follow-Up

9.4.1 Follow-up Period and strategy

Follow-up visits will be completed by special persons for all cases selected in this study .All patients are followed up with 30 days, Recommend patient follow-up every 3 months during the first 2 years and then every 6 months beyond the third year (1、 3、 6、 9、 12、 15、 18、 21、 24、 30 and 36 months after the operation),and record with patients’ consent. This study suggests that the above examinations should be conducted in the patient's primary surgical research center, but does not exclude outer court review. For Outer Court review, It recommended that visiting the hospital as a three-level hospital, and these information will be recorded by the follow-up specialist. The occurrence of tumor recurrence or metastasis and the survival status of all patients are evaluated and recorded according to the results of the various examinations. Patients who refuse to follow the protocol should be recorded as lost to follow-up, and at the end of the study, these cases should be analyzed together with cases lost to follow-up in line with the criteria of this study.

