10.1 Statistical analysis plan

- Statistical software: we will use SPSS statistical software, version 23.0 (SPSS Inc), and the R software environment (R Foundation for Statistical Computing) to perform statistical analyses.
- Basic principle: The method of differential testing was adopted. The safety population of the study consists of the patients who receive safety evaluation data after the intervention. Descriptive statistics and two-sided tests were conducted for the safety indicators and the incidence of adverse reactions. A p-value <0.05 is considered statistically significant. The confidence interval of the parameters is estimated with a 95% confidence interval.
- Shedding analysis: Total shedding rate of two groups and loss rate due to adverse events will be compared using pearson χ^2 test

- All data analyses will be conducted on a per-protocol (PP) basis.
- Method of outlier determination: the observation value is greater than P75 or less than P25, and the exceed value more than 3 times of the quartile spacing ($=p75-p25$), which will be sentenced to outlier data. During the analysis, the sensitivity analysis is used for outlier data, namely analyzing outcomes including or excluding outlier's data. and if the results are not contradictory, the data is retained; if the contradiction, it depends on the specific circumstances.
- Descriptive statistics: The measurement data gives the mean, the standard deviation and the confidence interval, and the minimum value, the maximum value, the P25, the median and the P75 are given when necessary; matched data also gives the mean and standard deviation of the gap-value, and the median and average rank of the Non-parametric method. The nominal-scale data gives the frequency distribution and the corresponding percentages. The level data gives the frequency distribution and the corresponding percentages, as well as the median and the average rank. Qualitative data give positive rate, positive number, and denominator numbers. The survival data gives the number of events, the number of deletions, the median survival time, and the survival rate.
- Subgroup analysis : Sub-group analysis is to find the factors that may affect prognostic according to the specific circumstances of the data.
- Missing values handling: This study does not fill in missing values

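### The per-protocol, no-imputation rule lets outcome-related losses leave the primary comparison, and no stated analysis tests what that does to the non-inferiority conclusion

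*Protocol*

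**What the plan says.** - **Missing values.** Section 10.1 states "This study does not fill in missing values". The Summary (Statistical considerations) repeats this. Both places also put all analyses on a per-protocol basis.
- **Sensitivity analysis.** The only one named, in the Summary and in 10.1, compares results with and without outlying values. It is defined through quartiles and so has no use for a yes/no complication endpoint.
- **Withdrawal.** Section 4.3 lists, among other reasons, patients who quit of their own accord at any stage and patients whose severe perioperative complications prevent the planned treatment.
- **Refusal.** Section 9.4.1 states "Patients who refuse to follow the protocol should be recorded as lost to follow-up" and has them analysed with the lost cases at the end of the study. It does not say how, or whether complications already on file are retained.
- **Check on losses.** Section 10.1: "Total shedding rate of two groups and loss rate due to adverse events will be compared using pearson" (the chi-square test).
- **Planned loss.** Section 3.3: "Considering that the maximum detachment rate of this clinical study was 10" per cent, which takes 68 per group to 75.
- **Endpoint.** Section 8.1.3 limits postoperative complications to 30 days, or to first discharge if the stay is longer. Sections 8.1 and 8.1.2 take every operated patient as the denominator.

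**The concern.** The design is open and non-randomized, and the primary question is whether robotic surgery has a complication rate no more than 15 points above laparoscopic surgery. Some of the reasons for leaving the analysis set are themselves complications, or may follow from one. If such patients drop out of the comparison, the arm that loses more of them looks safer than it was. In a non-inferiority test, a loss of this kind in the robotic arm pushes towards a false claim of non-inferiority.

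The protocol's stated rules do not address this. They apply per-protocol to all analyses and fill in nothing. The one comparison of losses looks at how many patients left, not at how the complication difference would change if they were counted. Equal loss in both arms would pass that test whatever happened to the patients who left.

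**Working it through.** **Inputs from section 3.3.** Control: "the postoperative complication rate of laparoscopic total gastric surgery is about 15" per cent. Robotic: "postoperative complication rate of the study group was similar to the control group". Margin 15 points, alpha 0.05, power 80%. Evaluable: "the sample size of each group was 68 cases". Enrolled: 75 per group.

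**The plan's own figure.** The normal approximation at one-sided 0.05 gives n = (1.645 + 0.842)² × 2 × 0.15 × 0.85 / 0.15² = 70.07, so 71. Exact enumeration of the unpooled Z test at one-sided 0.05 first reaches 80% at n = 68 (power 0.8003), so 68 is reproduced. For loss, 68 × 1.10 = 74.8, hence 75, and 75 − 68 = 7 planned losses per group.

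**Which interval.** The sample size fits a one-sided 0.05 test. The Summary makes all tests two-sided and 10.1 gives 95% intervals. Both readings are shown.

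**Assumptions that the protocol does not give.** Observed complications are 10/68 in each arm (14.7%, close to the planned 15%). All 7 losses per arm have unknown status. Of these, *j* robotic and *c* laparoscopic patients had a complication.

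**Formula.** Wald upper limit for robotic minus laparoscopic: p₁ − p₂ + z√[p₁(1−p₁)/n + p₂(1−p₂)/n], with z = 1.96 (two-sided 95%) or 1.645 (one-sided 95%).

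Complete case: SE = √(2 × 0.1471 × 0.8529 / 68) = 0.0607. The limit is 1.96 × 0.0607 = 11.9 points, or 1.645 × 0.0607 = 10.0 points. Both are below 15.

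After restoring the lost patients, p₁ = (10 + j)/75 and p₂ = (10 + c)/75:

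| j v c | Difference (points) | SE (points) | Two-sided 95% limit | One-sided 95% limit |
|---|---|---|---|---|
| 1 v 1 | 0.0 | 5.78 | 11.3 | 9.5 |
| 2 v 0 | 2.7 | 5.77 | 14.0 | 12.2 |
| 3 v 1 | 2.7 | 5.98 | 14.4 | 12.5 |
| 3 v 0 | 4.0 | 5.87 | **15.5** | 13.7 |
| 4 v 1 | 4.0 | 6.08 | **15.9** | 14.0 |
| 4 v 0 | 5.3 | 5.97 | **17.0** | **15.15** |
| 5 v 1 | 5.3 | 6.17 | **17.4** | **15.5** |
| 7 v 0 (worst case) | 9.3 | 6.23 | **21.5** | **19.6** |

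Bold marks a limit above the margin.

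**What the planned loss comparison would show.** Total loss of 7/75 v 7/75 gives Pearson p = 1.00 in every row. If the losses with complications are recorded as due to adverse events, Pearson gives p = 0.043 at 4 v 0, 0.080 at 3 v 0 and 0.17 at 4 v 1. It can therefore flag some imbalances, but it gives no estimate of the complication difference.

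**The other denominator.** If lost patients stay in the all-operated denominator of 8.1 with nothing filled in, they count as free of complications: 10/75 v 10/75, two-sided limit 1.96 × 5.55 = 10.9 points. The limit looks better than the complete-case one although nothing more is known.

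**The case against.** The case on the other side has real weight.

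- **Most of the primary outcome is collected in hospital.** Section 9.3.4 records complications from the first postoperative day to discharge, 11.1.1 asks for the discharge form within three days, and 12.2 wants complete collection of adverse events for 30 days. Section 9.4.1 covers follow-up to 36 months. A reader might infer that it erases complications already known, but it does not say so; it fails to say that they are kept. The point matters for the primary outcome only when refusal falls inside the primary window.
- **The 10% is not a count of missing outcomes.** Section 3.3 does not define detachment, and many withdrawals under 4.3 (T4b, M1, unresectable disease, simultaneous surgery) may have a known complication status. Seven unknowns per arm is an upper bound. This stands.
- **The reversing splits are extreme.** Four of 7 is 57%, against a planned 15%, and the one-sided limit then passes the margin by only 0.15 points. This stands too.
- **A check on losses exists.** A reader might infer that the plan has none, or that Pearson should give way to Fisher's exact test. Neither follows. The comparison of adverse-event losses would flag 4 v 0 with Pearson (p = 0.043) but not with Fisher (p = 0.12), and the Summary already allows Fisher where appropriate.
- **A separate SAP is cited at the end of 10.1.** It could add detail, and declining to impute is an acceptable primary rule. But the protocol itself makes all analyses per-protocol with nothing filled in. As written, that leaves no room for an all-operated or imputed check, so the point does not rest on silence.

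**Conclusion.** The concern holds in a limited form. The stated rules allow outcome-related loss to leave the primary comparison, and the loss-rate test does not show whether the non-inferiority conclusion survives it.

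With the assumed 10/68 in each arm and all 7 planned losses per arm unknown, the conclusion changes at 3 v 0 or 4 v 1 (two-sided 95%) and at 4 v 0 or 5 v 1 (one-sided 95%). It stands at 1 v 1 and 2 v 0 on either reading. A reader might infer that the permitted loss will overturn the result. The documents do not support that: reversal needs unequal, outcome-related loss inside the primary window, and the number of truly unknown outcomes is likely to be below 7 per arm. This is a correction worth making, not evidence that the trial will mislead.

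**What to change.** In 10.1, with a matching clarification in 9.4.1:

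1. Any complication recorded within the primary window before loss, refusal or withdrawal counts as an event. The patient stays in the all-operated denominator of 8.1 and 8.1.2 for at least a sensitivity analysis. This also covers patients with known outcomes whom the per-protocol rule removes, whom an analysis of unknown outcomes alone would miss.
2. The primary outcome is missing only if status at 30 days (or at first discharge, if later) is truly unknown. Refusing later visits does not make it missing.
3. Add a tipping-point analysis of the primary outcome against the 15-point margin, with the same interval as the primary comparison. It should include the worst case for the robotic arm (all its missing outcomes counted as events, laparoscopic ones as non-events) and report the splits at which the conclusion changes.

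The planned chi-square on losses can stay as a description. The cost is a few lines of text and a little more analysis, with no new data. The drawback is that the result may look less robust.

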11.1 Case Report Form (CRF)

11.1.1 CRF Types and Submission Deadline

CRFs used in this study and their submission deadlines are as follows:

- (1) Case Screening: 1-7 days prior to surgery (time frame of three days)
- (2) Enrolling: submitted to the data center at one day prior to surgery
- (3) Surgery: within 1 day after surgery
- (4) Postoperative discharge: within three days after the first discharge
- (5) Follow-up records: 7 days after each specified follow-up time point

11.1.2 Method of transmission of CRF

In this study, the paper CRF form are used for information and data transmittal.

11.1.3 Revision of CRF

After the start of the study, if the CRF is found to lack items that are then deemed pertinent, under the premises of ensuring the amendment of the CRF does not cause medical and economic burden and increased risks to the selected patients, the CRF can be modified after the Research Committee adopt it through discuss at the meeting. If the amendment of the CRF requires no changes to this study protocol, the latter will not be modified.

11.2 Monitoring and Supervising

To assess whether study implementation follows protocol and data are being collected properly, monitoring should be conducted every February during the follow-up period. Monitoring is to complete through visiting a hospital and comparing the original Data.

12 Relevant Provisions on adverse events

12.1 Various forms of adverse events caused by original incidence

Adverse events relating to various forms of deterioration in primary diseases should be recorded according to Short Name of CTCAEv4.0.

12.2 Evaluation of adverse events

- Evaluation of adverse event/adverse reaction are based on [Accordion Severity Grading System] and [CTCAE v4.0].
- Adverse events will be graded 1 ~ 5 as per definition. For treatment-related death, fatal adverse events are classified as Grade 5 in the original CTCAE
- Toxicity items specified in the [surgery-related adverse events], Grade and the discovery date of Grade should be recorded in the treatment process report. For other toxicity items observed, observed Grade 3 toxicity items are only recorded in the

freedom registration column of the treatment process report, as well as Grade and the discovery date of Grade. Grade recorded in the treatment process report must be recorded in the case report form.

- CTCAE v4.0, the so-called “Adverse Event”, “all observed, unexpected bad signs, symptoms and diseases (abnormal value of clinical examination are also included) in the treatment or disposal, regardless of a causal relationship with the treatment or handling, including determining whether there is a causal relationship or not”.
- Therefore, even if events were “obviously caused by primary disease (cancer)” or caused by supportive therapy or combination therapy rather than the study regimen treatment (protocol treatment), they are “adverse events”.
- For adverse event data collection strategy, the following principles should be complied with in this study:1) Adverse events within 30 days from the last treatment day of the study regimen treatment (protocol treatment), regardless of the presence or absence of a causal relationship should be completely collected. (When adverse events are reported, the causality and classification of adverse events are separately discussed) 2) Adverse events within 30 days from the last treatment day of the study regimen treatment (protocol treatment), regardless of the presence or absence of a causal relationship should be completely collected. (When adverse events are reported, the causality and classification of adverse events are separately discussed)

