9.5.2 Postoperative adjuvant chemotherapy

This study uses a combination of chemotherapy based on 5-FU (5-fluorouracil) and recommends the SOX regimen.

In cases of good physical and tolerable conditions, chemotherapy is first started within 3-4 weeks after surgery and then according to the regularity of the chemotherapy cycle.

During the chemotherapy period, tumor recurrence should be assessed according to the follow-up plan.

When tumor recurrence occurs during chemotherapy, the adjuvant chemotherapy regimen of this study is discontinued. The follow-up treatment is decided by the research center according to the clinical treatment routine. This study does not make regulations, but the cause and follow-up treatment plan should be recorded in the CRF.

Adjuvant chemotherapy requires written approval from the patient.

Subjects that refuse postoperative adjuvant chemotherapy or do not complete the adjuvant chemotherapy are not excluded from this study, but the cause is marked and recorded in the CRF.

Patients who choose adjuvant chemotherapy, irregular chemotherapy, or a non-first-line regimen are not excluded from the study, but Safety Evaluation Committee is obliged to monitor patient safety during follow-up. The patient's chemotherapy medication must be recorded in the CRF.

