12.3.1.2 Adverse Events with Regular Reporting Obligations

One of the following adverse events are regular reporting objects:

- (1) After 31 days from the last treatment day, deaths for which a causal relationship with treatment cannot be denied, including suspected treatment-related death; death due to obvious primary disease is included.
- (2) Expected Grade 4 non-hematologic toxicity (CTCAE v3.0 adverse events other than the blood/bone marrow group).
- (3) Unexpected Grade 3 adverse events: Grade 3 adverse events are not recorded in the 12.1 expected adverse events.
- (4) Other significant medical events: adverse events that the study group deems cause important and potentially permanent, significant impact on their offspring (MDS myelodysplastic syndrome, except for secondary cancer) Adverse events among above (2)-(4), determined to have a causal relationship (any of definite, probable, possible) with the study regimen are regular reporting objects.

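### Section 12.2 requires complete adverse-event collection but gives unlisted toxicity a recording place only at Grade 3, states one collection rule twice, and leaves the start of its 30-day window undefined

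*Protocol*

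**What the plan says.** Section 12.2 defines an adverse event broadly, abnormal test values included and irrespective of cause, and fixes the scale: "Adverse events will be graded 1 ~ 5 as per definition". Its collection strategy has two numbered principles. Each says that events in the 30 days after the last day of protocol treatment, "regardless of the presence or absence of a causal relationship should be completely collected". The second opens "2) Adverse events within 30 days from the last treatment day of the study regimen treatment (protocol treatment" and repeats the first word for word.

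For recording, the section separates a bracketed list of surgery-related events from everything else. Listed items are recorded with their grade and date. For the rest, "For other toxicity items observed, observed Grade 3 toxicity items are only recorded in the" free-entry column of the treatment process report (the sentence runs over a page break). The link to the CRF is "Grade recorded in the treatment process report must be recorded in the case report form".

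Section 12.3.1.1 makes two things emergency reports: any death during treatment or within 30 days of the last treatment day, and unexpected treatment-related Grade 4 non-hematologic toxicity. Section 12.3.1.2 makes expected treatment-related Grade 4 non-hematologic toxicity a regular report, and also "After 31 days from the last treatment day, deaths for which a causal relationship with treatment cannot be denied".

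The groups in Section 3.2 are defined by the operation alone. Section 9.5.1 nevertheless gives chemotherapy under the protocol's own provisions to R0 patients of stage II and above. Section 9.5.2 says that on recurrence "the adjuvant chemotherapy regimen of this study is discontinued".

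**The concern.** Three drafting faults sit in one rule, and they differ in kind. The grade sentence conflicts with complete collection. The repeated principle is a duplication that probably displaced another rule. The undefined treatment is an ambiguity about when the window opens and closes.

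Two things depend on them. Section 10.1 promises adverse-event incidences and listings, and these change with the sentence the research staff follow and the day they count from. The reporting duties of Section 12.3 change with the same day. The trial is open and non-randomized and safety is its stated aim, so discretion over what is written down could differ between arms.

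**Working it through.** The protocol gives no figure on this point to reproduce. The check is a comparison of sections plus date arithmetic.

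**1. Collection against recording (12.2)**

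- Collection: all events in the window, no grade threshold, grades 1 to 5.
- Recording of unlisted toxicity: Grade 3 named, in the free-entry column. No sentence in 12.2 covers Grades 1, 2, 4 or 5.
- CRF: must carry the grades that the treatment process report holds.

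The word *only* can be read in two ways. If it limits the grade, the rule excludes the other grades and flatly contradicts complete collection. If it limits the place, Grade 3 items go to the free-entry column and the other grades are simply not provided for. On either reading 12.2 gives unlisted events of other grades no recording place, while 12.3.1.1 and 12.3.1.2 expect Grade 4 events and deaths to be reported.

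**2. Principles 1) and 2) (12.2)**

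The texts are identical, so the list contains one rule. Section 12.3.1.2(1) deals with deaths from day 31, and no collection principle in 12.2 matches it. That makes a rule for later events a plausible candidate for the lost item, but the protocol does not say what it was.

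**3. The start of the window**

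Inputs: 30-day window (12.2); chemotherapy starts 3-4 weeks after surgery (9.5.2), taken here as days 21-28; follow-up ends on 2021.02.08, after enrolment closes on 2021.01.08 (3.5).

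- Surgery as anchor: the window closes on postoperative day 30. The part after the start of chemotherapy is 30 − 28 = 2 to 30 − 21 = 9 days.
- Chemotherapy as anchor: even if the first chemotherapy day were also the last, the window closes no earlier than 21 + 30 = day 51 to 28 + 30 = day 58. Each further cycle moves it later.
- Stated follow-up after the last enrolment: 2021.01.08 to 2021.02.08 = 31 days. This roughly fits the surgery reading and is too short for the chemotherapy reading in the last patients enrolled.

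On the chemotherapy reading the window also varies by patient. Only R0 patients of stage II and above are due chemotherapy (9.5.1), and those who refuse it stay in the study (9.5.2). The length of the adverse-event window would then depend on pathology and on choices made after surgery. The protocol does not give the share expected to receive chemotherapy, so the effect on the tables cannot be sized.

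**4. Reporting consequence**

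Take a death in a late chemotherapy cycle.

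- Chemotherapy counted as protocol treatment: an emergency report regardless of cause (12.3.1.1), first report within 72 hours (12.3.2.1).
- Surgery alone counted: more than 30 days after the last treatment day, so a regular report if a link to treatment cannot be denied (12.3.1.2), due within 15 days (12.3.2.2).

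**The case against.** The strongest reply is that other sections catch most of what matters. Section 9.3.4 has postoperative complications recorded on Clavien-Dindo I to V, with a closing category for any other new complication. Section 8.2 counts every death within 30 days whatever the cause. Section 9.5.3 records performance status, CTCAE items and blood tests around each chemotherapy cycle. Section 12.3 requires its own reports. This stands. A reader might infer from 12.2 that four of the five grades of any unlisted event go unrecorded in the trial. The protocol as a whole does not support that; the gap is in the adverse-event recording rule.

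A reader might likewise infer that nothing governs events after day 30. That also fails. Section 12.3.1.2 covers later deaths and sets no 30-day limit for its other items, Section 9.3.4 defines long-term complications to 3 years, and Section 9.4.1 recommends visits to 36 months.

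On the anchor, it can be argued that surgery is clearly meant: the groups are surgical, the outcome window is about a month, and 12.2 itself contrasts protocol treatment with combination therapy. This makes surgery the likelier reading but does not settle it, because Sections 9.5.1 and 9.5.2 describe the chemotherapy as the study's own regimen and no definition excludes it.

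Finally, the primary endpoint has its own window from surgery (8.1.3) and its own complication list (9.3.4). It and the sample size are untouched. This stands in full.

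**Conclusion.** Section 12.2 is internally inconsistent and should be corrected. Complete collection cannot be carried out under a recording rule that provides for unlisted toxicity only at Grade 3. One of the two collection principles carries no content. The 30-day window has two possible anchors, with closing days of 30 against 51-58 or later.

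The effect is limited to the adverse-event incidence tables and to reporting duties. It does not reach the primary comparison, and many severe events are recorded elsewhere in the protocol. The conclusion rests on the wording of 12.2 and on reading 3-4 weeks as days 21-28. No difference between arms has been shown, and none can be computed from the protocol.

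**What to change.** 1. Reword the recording sentence in 12.2 so that unlisted events of every grade, explicitly including Grades 4 and 5, go into the treatment process report and the CRF within the 30-day window. This matches the collection principle.
2. Delete the duplicate principle 2) or restore the rule that was intended, and reconcile it with 12.3.1.2(1) on deaths from day 31. The sponsor must supply the content; it cannot be inferred from the protocol.
3. Define the last day of protocol treatment once, for both 12.2 and 12.3, stating whether chemotherapy under 9.5 is included.
4. For comparing the arms, tabulate events within 30 days of the operation, in line with 8.1.3 and 8.2. Keep this analysis window separate from the reporting clock. Moving the 12.3.1.1 clock to the operation could remove the 72-hour report for deaths in later chemotherapy cycles, and 9.5.3 contains no reporting deadline to replace it. Emergency reporting of deaths should not be narrowed.

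The cost is a few sentences in 12.2 and 12.3 and somewhat more adverse-event recording per patient.
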